### **30 day Follow Up:**

We aim to follow up with the participants after 30 days of initial study completion. For Group 1 participants this period coincides with Group 2 study completion surveys at 60 days, whilst group 2 will receive these follow up surveys at 30 days after their study period completion (i.e. at 90 day time point).

These follow up surveys include the baseline surveys, i.e. the same set of questionnaires administered as a part of the study. In addition, a set of compliance questions aimed at collecting information on whether or not IEO was practiced post the study period and its perceived effectiveness in participant's life with possible reasons for non-compliance are included in this follow up questionnaire.

### **Final Survey:**

These surveys are being sent out after the study analysis has been completed and aim's to look at long term compliance to (IEO) intervention and its impact on the participants lives. The survey captures both qualitative and quantitative data on how the study has impacted their lives and provides information on the study acceptance.

### **Questionnaires:**

The following questionnaires are incorporated into the study survey and will be administered to the study participants at the aforementioned time points.

***Mindfulness Attention Awareness Scale (MAAS):***

MAAS is a 15 question validated instrument that assesses mindfulness and attention while performing routine activities of daily living. Participants are asked to rate on a scale of 1 (Almost Always) to 6 (Almost Never) to assess the frequency of occurrence of each experience. Mean is then computed using items from each of the 15 questions to create a MAAS score.

***Perceived Stress Scale (PSS):***

PSS is a 10 question validated instrument that assesses stress. Participants are asked to rate on a scale of 0 (never) to 4 (very often) how often they agree with various statements. Items from each of the 10 questions are then summed to create a total perceived stress score.

***Maslach Burnout Inventory - General Services Survey (MBI)***

This survey consists of 16 questions across three dimensions: exhaustion, cynicism, and professional efficacy. Each question is scored on a scale from 0 (never) to 6 (everyday). The points from each dimension are added to provide a total score for that dimension. Average scores for each dimension are also computed.

***Dispositional Positive Emotion Scale- Joy Subscale (DPES-Joy)***

The joy subscale of DPES is a 6 item questionnaire that measures a dispositional tendency to feel joy in life. Participants report their level of agreement to each item on a scale of 1 (Strongly agree) to 7 (Strongly disagree). Mean is computed for the combination of all 6 items.

***Centre for Epidemiological Studies: Depression Scale (CES-D)***

This scale aims to measure depressive symptomatology and consists of 20 questions on how the participant felt or behaved in the past week. The questions are rated on a scale of 1 (Rarely or none of the time, less than 1 day) to 4 (Most or all of the time, 5-7 days). Possible range of scores is 0-60 with higher scores indicating the presence of more symptomatology.

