***Emotional Distress and Anxiety Short Form- 7 Item Questionnaire measuring Anxiety***

This is a short survey used to assess for anxiety in participants. The questionnaire includes 7 questions which are rated on a scale of 1 (Never) to 5 (Always). Sum is computed for the responses and scores range between 7-35, with higher scores indicating greater severity of anxiety.

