### b. *Data Analysis:*

Baseline characteristics of participants will be recorded. Continuous data will be presented as means  $\pm$  standard deviation or median (interquartile range) depending on the distribution of the data and assessed with a parametric or non-parametric t-test, as appropriate. Normality will be assessed with the Shapiro-Wilk test. Categorical data will be presented as frequencies and proportions and assessed with a chi-square or Fisher's exact test. SAS 9.4 (SAS Institute Inc., Cary, NC) will be used for all analyses with two-sided p-values  $< 0.05$  considered statistically significant.

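### Does the mismatch between CES-D items rated 1 to 4 and a stated total of 0-60 call for a change to the plan?

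*Combined protocol and SAP*

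**What the plan says.** The combined protocol and SAP describes its instruments in section B3.A, under Questionnaires. According to the CES-D entry, the scale "consists of 20 questions on how the participant felt or behaved in the past week". On the response format it says: "The questions are rated on a scale of 1 (Rarely or none of the time, less than 1 day) to 4". On the total it says: "Possible range of scores is 0-60 with higher scores indicating the presence of more symptomatology". It does not say how the item ratings become the total, and no other section describes CES-D scoring.

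The other instruments each have a scoring step:

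- PSS: "Items from each of the 10 questions are then summed to create a total perceived stress score".
- Anxiety short form: "Sum is computed for the responses and scores range between 7-35".
- MBI: items are added within each of three dimensions.
- MAAS and DPES-Joy: items are averaged.

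Section B3.B.b (Data Analysis) is generic. "Continuous data will be presented as means" with standard deviations, or as medians with interquartile ranges, and tested parametrically or non-parametrically. The Aim 2 and Aim 3 analyses compare scales by t-type tests, optional linear regression and paired tests. None of these sections names the CES-D or sets a threshold on it.

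**The concern.** The response codes and the total range cannot both describe a plain sum. The CES-D is also the only instrument in the list without a stated scoring step, so the reader cannot tell how the two figures connect.

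Four readings are open:

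- the 1-to-4 wording is a slip;
- the 0-60 range is a slip;
- a recode was left out;
- 1 to 4 are the labels participants see, while 0 to 3 is what is stored.

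The documents do not settle which is right.

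What is at stake is the reported CES-D level. If raw 1-4 codes were summed and the result read on the stated scale, every mean or median would look 20 points worse than it is. A single published value between 20 and 60 would not show which scoring had been used.

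**Working it through.** **Inputs** (all from the Questionnaires part of section B3.A)

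- CES-D: 20 items, lowest rating 1, highest rating 4, stated total 0-60.
- Anxiety short form, as a check on the method: 7 items rated 1 to 5, stated total 7-35.

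**Formula.** A sum of k items, each between a and b, runs from k × a to k × b.

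**Check on the method.** Anxiety form: 7 × 1 = 7 and 7 × 5 = 35. This matches the stated range.

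**CES-D as printed.** 20 × 1 = 20 and 20 × 4 = 80. The stated 0-60 is not reproduced.

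**Could another scoring rule give 0-60?**

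- Reverse-keying r items as 5 − x: the minimum is (20 − r) × 1 + r × (5 − 4) = 20, and the maximum is (20 − r) × 4 + r × (5 − 1) = 80. The range stays 20-80 for any r.
- Item mean: 1 to 4.
- Subtracting 1 from each item: 20 × (1 − 1) = 0 and 20 × (4 − 1) = 60. This matches.

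The two totals have the same width (80 − 20 = 60 − 0 = 60). On a complete form, raw total = recoded total + 20.

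**What the 20 points do to the planned analyses.** Write A and B for the group means on the 0-60 scale.

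- Between groups: (A + 20) − (B + 20) = A − B.
- Paired change: (follow-up + 20) − (baseline + 20) = follow-up − baseline.
- Standard deviation, ranks and the Shapiro-Wilk statistic do not change when a constant is added, so the t-test, its non-parametric counterpart and their p-values are unchanged.
- Linear regression: the group coefficient is unchanged, with or without baseline CES-D as a covariate. Only the intercept can move.
- Reported mean or median: + 20, which is 20/60, or one third of the stated range.

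**Conditions for exact invariance.**

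- With u items unanswered and a plain sum of those answered, the offset on that form is 20 − u. If the groups differ by one unanswered item on average, the group difference moves by 1 point.
- If a share p1 of one group's forms and p2 of the other's were coded 1-4 and the rest 0-3, the group difference would move by 20 × (p1 − p2). For illustration only, shares differing by 0.10 would give 20 × 0.10 = 2 points. The documents give no sign of mixed coding.

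**Can the coding be recognised from the data?** An individual complete total below 20 can only come from 0-3 items, and one above 60 only from 1-4 items. The ambiguity between 20 and 60 concerns a lone summary value, not an analyst holding the item data.

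**The case for a change.** The strongest case for acting has three parts.

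First, levels are reported as well as differences, and 20 points is a third of the scale. That size is correct, but the error requires an analyst to sum the raw codes and ignore the range given in the next sentence. That the CES-D level will be reported at all is a fair inference from the general wording of section B3.B.b. Depression is not named in any aim.

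Second, the sample size section says these data will help to power a larger trial, so outcome definitions ought to be unambiguous. A power calculation draws on the difference and the standard deviation, and both are the same under either scoring.

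Third, the Study Procedure text allows paper or online completion. If the two modes carried different codes, or partly answered forms were summed as they stood, the offset would not be constant. That qualification stands, and the claim of no effect has to be stated with it. It is a reason for the data manager to look at the stored codes when programming the score. It is not evidence of bias in the plan.

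It also stands that the entry contradicts itself and that a sentence on coding and summing would be tidier. That sentence would record what an analyst has to establish from the data dictionary anyway.

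**Conclusion.** The contradiction is confirmed: 20 items at 1 to 4 give 20-80, not 0-60, and nothing else in the document reconciles them. It is a clerical slip or an omitted scoring detail, and no change to the plan follows. With complete forms coded alike, the effect on every planned comparison is exactly zero. The possible effect on a reported level is 20 points, conditional on raw codes being summed.

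Three of the four readings lead to the stated 0-60 scale. The fourth, in which the range is the slip, would shift the reported level and leave the comparisons alone. No cut-off, stopping decision or sample size uses the score; the minimum of 60 participants is a feasibility figure unrelated to the scale maximum.

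The conclusion rests on uniform coding across paper and online forms and on complete responses (or a missing-item rule that respects the coding). The documents neither confirm nor contradict either assumption.

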***Emotional Distress and Anxiety Short Form- 7 Item Questionnaire measuring Anxiety***

This is a short survey used to assess for anxiety in participants. The questionnaire includes 7 questions which are rated on a scale of 1 (Never) to 5 (Always). Sum is computed for the responses and scores range between 7-35, with higher scores indicating greater severity of anxiety.

**IEO Activity Diary:**

The IEO activity diary is a tool which helps the participants to keep a track of their activities each week. This enables the study team to measure compliance and protocol adherence by the participants.

**Reading Log:**

The reading log is a tool which helps the participants to keep a track of their reading each week. This enables the study team to measure compliance and protocol adherence by the participants.

## B. Statistical Considerations

### a. *Sample Size Justification:*

In this survey based, randomized cross-over study, we are looking at the feasibility of implementing an Inner Engineering Online Intervention on a group of willing company employees. Since it is a feasibility study, we plan to enroll a minimum of 60 participants. Data from these participants will be used to power a larger trial based on the outcomes such as stress, burnout & overall well-being measured during the course of the study.

### b. *Data Analysis:*

Baseline characteristics of participants will be recorded. Continuous data will be presented as means  $\pm$  standard deviation or median (interquartile range) depending on the distribution of the data and assessed with a parametric or non-parametric t-test, as appropriate. Normality will be assessed with the Shapiro-Wilk test. Categorical data will be presented as frequencies and proportions and assessed with a chi-square or Fisher's exact test. SAS 9.4 (SAS Institute Inc., Cary, NC) will be used for all analyses with two-sided p-values  $< 0.05$  considered statistically significant.

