#### **Analysis of Aim 2:**

Given the continuous nature of the scales used to assess stress, burnout and measures of well-being, differences between groups will be assessed with a parametric or non-parametric t-test. Although we expect that randomization should account for any differences between baseline characteristics, unadjusted and adjusted linear regression may be utilized in order to account for differences that persist. Our primary analyses will be assessed using intention-to-treat principles. In order to assess whether there are differences between baseline and at six weeks, we will employ the use of paired t-tests as appropriate.

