#### **Analysis of Aim 3:**

To assess the effect of IEO intervention on the control group following its cross-over to the intervention will be assessed using a parametric or non-parametric t-test. Although we expect that randomization should account for any differences between baseline characteristics, unadjusted and adjusted linear regression may be utilized in order to account for differences that persist. Our primary analyses will be assessed using intention-to-treat principles. In order to assess whether there are differences between baseline and at six weeks, we will employ the use of paired t-tests as appropriate.

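### The observed distribution, not the plan, chooses between mean and median for each scale, so a mean difference, SD and confidence interval are not guaranteed for the outcomes meant to power the larger trial

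*Combined protocol and SAP*

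**What the plan says.** Section B3.B.b (Data Analysis) presents continuous data as mean and SD or as "median (interquartile range) depending on the distribution of the data and assessed with a parametric or non-parametric t-test", the choice being left to what is appropriate. The next sentence gives the only criterion in the document: "Normality will be assessed with the Shapiro-Wilk test". No cut-off is stated for that test. Nor is it stated whether it is applied per arm or pooled, at each visit, or to scores or changes. The inferential yardstick is a two-sided p-value below 0.05 being "considered statistically significant". No confidence interval is planned.

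The test choice is carried to the outcomes. For Aim 2, "differences between groups will be assessed with a parametric or non-parametric t-test". For Aim 3, the effect after cross-over "will be assessed using a parametric or non-parametric t-test". The non-parametric test is not named. Under Aim 1, continuous data are to be handled in the same way.

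Two mean-based analyses are mentioned, neither as a firm commitment. Under Aim 2, "unadjusted and adjusted linear regression may be utilized in order to account for differences that persist", and for change over time, "we will employ the use of paired t-tests as appropriate". Aim 3 has matching wording.

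Section B3.B.a (Sample Size Justification) sets a minimum of 60 participants on feasibility grounds and states the later use: "Data from these participants will be used to power a larger trial based on the outcomes such as stress, burnout & overall well-being".

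**The concern.** A feasibility trial that will feed a power calculation has estimation as its main statistical job. For continuous scales, the next trial's planners normally need an SD and a plausible mean difference with its uncertainty. Under this plan, a scale judged non-normal can be reported as medians, IQRs and a p-value, and the plan would have been followed.

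The second issue is consistency. The same questionnaires are given at baseline and 30 days to both groups, at 60 days to group 2, and again at follow-up. If the sample's apparent normality decides the summary, one scale may appear as a mean at one visit and a median at the next although its distribution has not changed. What is being estimated then depends on the sample and not on the question.

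**Working it through.** **Plan's own figure.** The minimum of 60 comes with no effect size, SD, power or dropout rate, so no formula can reproduce it. It is used below only as the sample size.

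**Inputs from the document.** At least 60 participants; two groups by simple randomization; the same scales repeated at two or more visits; two-sided 0.05 for all analyses.

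**Assumptions, because the document is silent.** About 30 per arm (no ratio is stated); a Shapiro-Wilk cut-off of 0.05; gamma-shaped scores, for which skewness = 2/√shape (shapes 16, 8, 4 and 2 give 0.5, 0.7, 1.0 and 1.4); between-visit correlation of 0.5 or 0.7 on the underlying normal scale; the same distribution at both visits, so any switch is chance alone. A bounded, right-skewed 0–60 shape (skewness 0.82) was added as an illustration. There were 4,000 runs per setting.

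**Step 1: how often the check rejects, and how often two visits are classed differently.**

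| Skewness | Rejects, n = 30 (per arm) | Visits differ, n = 30 | Rejects, n = 60 (pooled) | Visits differ, n = 60 |
|---|---|---|---|---|
| 0 (normal) | 5% | 9% | 5–6% | 8–10% |
| 0.5 | 14–16% | 22–23% | 25–27% | 32–36% |
| 0.7 | 23–24% | 30–33% | 48% | 41–47% |
| 1.0 | 44% | 41–45% | 79% | 28–33% |
| 1.4 | 75–76% | 30–36% | 98% | 4% |
| 0–60 shape, 0.82 | 54–55% | 39–47% | 92% | 13–15% |

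Rough check: if the visits were independent, they would differ with probability 2p(1 − p), where p is the rejection rate. At n = 30 and skewness 1.0 this is 2 × 0.44 × 0.56 = 0.49; the positive correlation lowers it to 41–45%. At n = 60 and skewness 0.5 it is 2 × 0.26 × 0.74 = 0.38, against 32–36% simulated.

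Switching is most frequent where rejection is near even odds. With strong skewness and pooled testing it largely disappears, because the check then rejects at nearly every visit. In that case the scale is consistently assigned a median, and the missing commitment to means is what remains.

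**Step 2: type I error.** In simulation the two-step rule (normality check, then t-test or rank test) kept type I error at about 4% to 6%.

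**Step 3: what a planner with only medians and IQRs would face.** Normal-approximation size per arm for a true effect of 0.5 SD, 80% power, two-sided 0.05: n = 2(1.96 + 0.84)²/0.5² ≈ 62.8, so 63. If the SD must be recovered as IQR/1.349, n is multiplied by (recovered SD/true SD)²:

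- skewness 0.7: 62.8 × 0.955 gives 60, real power 78%
- skewness 1.0: 62.8 × 0.910 gives 58, real power 77%
- skewness 1.4: 62.8 × 0.824 gives 52, real power 72%
- skewness 2.0: 62.8 × 0.663 gives 42, real power 63%
- 0–60 shape: 62.8 × 1.077 gives 68, real power 83%

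The error can go either way. It affects only someone who lacks the individual data.

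**The case against.** The strongest reply is that nothing is lost. The sample size section speaks of the participants' data, not of the published table. Section B8 (Data Security) keeps responses in REDCap under study IDs, so the team can compute any mean or SD it needs. That stands, and it confines Step 3 to outside planners. What it does not supply is a commitment to report these quantities.

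The optional regression would give mean differences, and both its unadjusted and adjusted forms are mean-based, so those two do not conflict with each other. A mismatch arises only if a rank test is taken as the unadjusted result. But the regression is discretionary and tied to baseline differences that persist; the paired t-tests are discretionary too.

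It can also be said that a mechanical switch for each scale and visit is not written down. This is right. It is the natural reading of adjacent sentences, and the wording leaves room for judgement. Unspecified judgement after seeing the data leaves the same gap. Likewise, a rank test is the usual meaning of the plan's non-parametric option, but the plan does not name one.

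Finally, a reader might infer that the CES-D will usually fail the check. The document gives its 0–60 range and no distribution, so this has no support there. At n = 60, a skewness of 0.5 to 0.7 leads to rejection in only about a quarter to a half of trials.

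**Conclusion.** The point holds as a gap in commitment. The choice of summary and test is left to the observed distribution, it reaches the outcome scales of Aims 2 and 3, and no section guarantees a mean difference, SD and confidence interval for every scale. That sits badly with the stated plan to power a larger trial. The chance of inconsistent summaries for one scale at two visits is about 20% to 45% for skewness 0.5 to 1.0 (individual settings ran from 22% to 47%). This rests on the assumed shapes, correlations, 0.05 cut-off and equal arms.

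Two stronger readings are not supported. One is that false positives are inflated: type I error stayed near its nominal level. The other is that disagreement between t-test and rank test measures the harm. At a true effect of 0.5 SD the two gave different verdicts at 0.05 in 8% to 20% of simulated trials, but that is a property of the two tests and would remain when both are reported. The harm is to consistent estimation. It is worth correcting because the correction is cheap, but it does not threaten the trial's validity.

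**What to change.** Amend Data Analysis and the Aim 2 and Aim 3 analyses as follows.

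- Remove the normality test as the selector of summary or test.
- For every scale and visit, report mean and SD by arm, adding median and IQR where the distribution is skewed.
- Aim 2: give the between-arm mean difference with its 95% CI as the main result for every scale.
- Aim 3: give the within-group mean change with its 95% CI for the crossed-over control group.
- Report a named rank-based test for every scale as a fixed sensitivity analysis, whatever the distribution: Wilcoxon rank-sum between arms, signed-rank within group.

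This changes analysis wording only; sample size, data collection and participant burden are unaffected. The downside is that a mean-based test can have less power than a rank test on strongly skewed scales. The fixed sensitivity analysis keeps that information in view.

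### Aim 2 compares the arms on eight scores, each called significant at two-sided 0.05, with no primary outcome, adjustment or exploratory label

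*Combined protocol and SAP*

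**What the plan says.** - **Significance rule.** Section B3.B.b (Data Analysis) states that SAS 9.4 "will be used for all analyses with two-sided p-values" below 0.05 "considered statistically significant". It makes no exception for any aim or outcome.
- **Tests.** Under Analysis of Aim 2, "differences between groups will be assessed with a parametric or non-parametric t-test". Regression is optional, and paired tests are to be used where appropriate.
- **Scores.** The Questionnaires section defines six instruments. For the mindfulness scale (MAAS), "Mean is then computed using items from each of the 15 questions to create a MAAS score". For the Perceived Stress Scale (PSS), "Items from each of the 10 questions are then summed to create a total perceived stress score". For the Maslach Burnout Inventory (MBI), "This survey consists of 16 questions across three dimensions: exhaustion, cynicism, and professional efficacy", and "The points from each dimension are added to provide a total score for that dimension"; no overall burnout total is defined. DPES-Joy, CES-D and the anxiety short form give one score each.
- **Primary.** The analysis sections use the word only for the analysis principle: "Our primary analyses will be assessed using intention-to-treat principles". No outcome is named primary.
- **Purpose.** The Sample Size Justification describes a feasibility study with at least 60 participants, whose data will be used to power a larger trial. Specific Aim 2 in section B2 is nonetheless a quantitative assessment of the effect of IEO.

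**The concern.** With eight between-arm tests, each judged at 0.05, the plan does not say which result answers Aim 2. A single score below 0.05 is significant under the plan's own rule, whichever score it is and whatever the other seven show.

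Two uses of the results are exposed. First, a chance finding on one score could be reported as IEO changing stress, burnout or well-being. Section B10 says that aggregate results go to the company and to the course provider. Second, the data are meant to power a larger trial. If that trial's outcome is whichever score crossed 0.05 here, the choice may rest on chance, and an effect estimate selected for being significant tends to be too large.

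**Working it through.** **Inputs**

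- Per-test level: two-sided 0.05 (Data Analysis). This is a stated rule, so there is no figure of the plan's to reproduce. The documents give no overall error rate.
- Number of scores: MAAS 1, PSS 1, MBI 3, DPES-Joy 1, CES-D 1, anxiety 1. Total 1 + 1 + 3 + 1 + 1 + 1 = 8.
- Correlation between scores: not in the documents. I assume a common value ρ and show 0 to 0.9.
- Arm size, for the checks only: 30 per arm, an assumed equal split of the minimum 60. Simple randomization does not guarantee that split.

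**Step 1. Independent scores.** If IEO affects no score, the chance of at least one p < 0.05 is 1 − 0.95^8 = 1 − 0.663 = 0.337.

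**Step 2. Correlated scores.** With common correlation ρ and c = 1.96, the chance is

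1 − ∫ φ(u) · [Φ((c − √ρ·u)/√(1−ρ)) − Φ((−c − √ρ·u)/√(1−ρ))]^8 du.

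Numerical integration is compared with a simulation of eight two-sample t-tests at 30 per arm (20,000 runs):

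| Common correlation | At least one of eight significant | t-test simulation |
|---|---|---|
| 0 | 33.7% | 33.5% |
| 0.3 | 30.0% | 29.9% |
| 0.5 | 25.0% | 25.3% |
| 0.7 | 19.1% | 19.7% |
| 0.9 | 11.9% | not run |

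These figures count a significant result in either direction. For independent scores, the chance of at least one in IEO's favour is 1 − 0.975^8 = 18.3%.

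**Step 3. What a primary outcome does, and whether a gate is needed.** Suppose one score is tested at 0.05.

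- *No gate.* The other seven are tested by Holm at 0.05 regardless of the primary result. When all eight are null, Holm's first step is 0.05/7 = 0.00714. For independent scores the overall error is 1 − 0.95 × (1 − 0.05/7)^7 = 1 − 0.95 × 0.951 = 9.6%. Simulation gives about 8% at correlation 0.5.
- *Gate.* The seven are tested only if the primary is significant. With no effect on any score, nothing is called significant unless the primary is, so the overall error is 5%.

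**Step 4. Price of the secondary threshold.** Using the noncentral t distribution with 58 degrees of freedom, 80% power, 30 per arm and no dropout, the detectable difference is 0.74 SD at 0.05 and 0.94 SD at 0.05/7. The normal approximation, (z for the level + 0.842) × √(2/30), gives 0.72 and 0.91.

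**The case against.** The best case for the plan is that this is a feasibility study. Its first aim is feasibility, the sample size has no efficacy power calculation, and section B4 says only that the results may inform other studies. Unadjusted tests on several candidate outcomes are common in that setting. This lowers the stakes, but the plan does not treat Aim 2 as descriptive: it assesses the effect of IEO and attaches a significance rule to it. One sentence labelling Aim 2 exploratory would meet most of the point, and that sentence is absent.

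Four stronger readings are tempting, and the documents do not support them.

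- *The plan promises 5% overall and fails to deliver it.* It makes no such promise. The 0.05 is a per-test level, and each single test keeps it. Nor does the plan say that one significant score establishes benefit. The gap is that it does not say which result would.
- *The overall error is at least 25%.* That floor needs an average correlation of about 0.5 or less. Stress, depression, anxiety and exhaustion scores may well overlap more than that.
- *All paired tests in both arms belong in the count.* The plan says only that paired tests are used where appropriate, not in each arm. A change over time in the control arm before crossover is not a false effect of IEO. The paired tests are also tied to the between-arm tests in a way that neither independence nor one common correlation describes.
- *Aim 2 can never be negative.* If IEO has no effect, between 1 − 0.337 = 66.3% (independent scores) and 1 − 0.119 = 88.1% (correlation 0.9) of trials would show no significant between-arm score.

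**Conclusion.** The concern holds for the eight between-arm comparisons of Aim 2. Followed as written, the significance rule gives a 12% to 34% chance of at least one significant score when IEO has no effect. The position in that range depends on the correlation between scores, which the documents do not give: 33.7% at 0, 25.0% at 0.5, 19.1% at 0.7 and 11.9% at 0.9. Every value is more than twice 5%.

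The figures assume no effect on any score, a common correlation, and one test per score. Aim 3 tests and optional regressions are not counted. The feasibility purpose means that this does not undermine the trial, but it should be corrected before the data are analysed.

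**What to change.** 1. **Analysis of Aim 2.** Before the data are analysed, name one primary efficacy outcome and contrast: IEO versus control at day 30, tested at two-sided 0.05. The PSS total is a reasonable candidate, since stress is a stated target and section B2 gives stress as the company's main reason for offering the course. The sponsor may prefer another score; section B1 lists burnout first. What matters is that one is named in advance.
2. **Other efficacy results.** Report the other seven scores, the paired comparisons and the Aim 3 comparisons as estimates with 95% confidence intervals, labelled exploratory.
3. **Optional.** If significance claims are wanted on the other seven scores, test them by Holm only after the primary is significant. Without that gate the overall error is about 8% to 10% at correlations of 0 to 0.5.
4. **Data Analysis.** For efficacy outcomes, limit the significance sentence to the primary contrast and any gated, Holm-adjusted secondary contrasts. Say separately whether the rule still applies to Aim 1 and baseline comparisons.

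The cost is wording only, with no new data, visits or participants. The primary keeps its 0.05 level. The downside is that fewer secondary scores can be called significant: at the strictest Holm step the detectable difference is 0.94 SD rather than 0.74 SD, assuming 30 per arm, 80% power and no dropout.
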